5.3 FURTHER ENDPOINTS

Safety:

Section 5.2.1 of the CTP: *Safety and tolerability of the investigational drug will be assessed based on:*

- *Adverse events (including clinically relevant findings from the physical examination)*
- *Safety laboratory tests*
- *12-lead ECG*
- *Vital signs (blood pressure, pulse rate)*
- *Local tolerability*

Section 5.2.1 of the CTP: *These parameters will be evaluated in a descriptive way only, and are therefore considered to be 'further parameters of interest'. A confirmatory analysis is not planned.*

5.4 OTHER VARIABLES

5.4.1 Demographic and other baseline characteristics

Section 5.2.5.2 of the CTP: *At screening, the medical examination will include demographics including height and body weight, smoking and alcohol history, relevant medical history and concomitant therapy [...].*

Age [years] will be determined as the difference between year of informed consent and year of birth.

BMI will be calculated as weight [kg] / (0.01 * height [cm])².

5.4.2 Pharmacogenomic evaluation

Section 5.3.1 of the CTP: *[..] a sample of at most 10 mL of blood will be taken at the screening examination if a subject's CYP2C19 genotype has not been previously determined. Pharmacogenetic results of CYP2C19 will be included in the final report.*

If a separate informed consent is signed, the extracted DNA of this sample will be used to determine a panel of genes coding for proteins that are involved in the Absorption, Distribution, Metabolism and Excretion (ADME) of drugs. The panel contains a list of known and likely functional variations present in key genes and covers more than 90% of the current ADME related genetic markers as defined by the PharmaADME group (website.pharmaadme.org). It is not intended to include these data in the final report. However, the data may be part of the report if necessary.

6. GENERAL ANALYSIS DEFINITIONS

6.1 TREATMENTS

For basic study information on investigational products, assignment of treatments, and selection of doses, please see CTP, Sections 3 and 4.

The study will be performed as a non-randomised, open-label, single arm, single period trial with 2 treatments (T and R).

In total, it was planned to assign up to 12 healthy male and female subjects (6 subjects with CYP 2C19 non-PM status and up to 6 subjects with 2C19 PM status).

For details of dosage and formulation see Table 6.1: 1 and Table 6.1: 2 below:

Table 6.1: 1 Treatments and labels used in the analysis of AEs, safety laboratory data and vital signs as well as demographics

Treatment	Short label
A BI 409306 50mg tab + 0.1mg i.v.	BI tab + iv

Table 6.1: 2 Overview of treatments for intra-individual comparison

Treatment	Short label
T BI 409306, 50 mg tablet, qd	BI 50mg tab
R BI 409306 (C-13/N-15), 0.1 mg/mL i.v. solution 0.1 mg, qd	BI 0.1mg iv

The following separate study phases will be defined for the analyses of AEs:

- **Screening** (ranging from 0:00 h on day of informed consent until first administration time of study drug)
- **On treatment** (including residual effect period (REP);
- **Follow-up** (ranging from end of on treatment phase until 0:00 h on the day after trial termination date)

Displays of AEs will be presented without differentiation of intravenous or oral administration during on treatment phase.

Two types of AE displays will be provided in the report:

A) Section 15.3 and Appendix 16.1.13.1.8 (for ClinicalTrials.gov and EudraCT only) of the CTR displays:

In these displays, the on treatment phase will be analysed (labelled with the name of the study treatment (short label)). Screening and follow-up periods will not be included in this analysis.

B) Section 15.4 and Appendix 16.1.13.1.8 (except for ClinicalTrials.gov and EudraCT) of the CTR displays:

- Screening
- On treatment (labelled with the name of the study treatment (short label))
- Follow-up

In Section 16.1.13.1.8 AE tables, the following totals will be provided in addition:

- a total over all study phases ("Total")

Tables of vital signs and laboratory values will present results by the above mentioned on treatment phase.

For detailed information on the handling of the treatments in the O*C views refer to Technical TSAP ADS plan. In particular, AEs will be counted for treatment if they occur up to the end of the residual effect period (REP) of 24 hours after oral administration.

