6.7 BASELINE, TIME WINDOWS AND CALCULATED VISITS

For vital signs and laboratory parameters the baseline is defined as the last measurement prior to first study drug administration.

Section 6.1 of the CTP: *Exact times of measurements outside the permitted time windows will be documented. The acceptable time windows for screening and end-of-trial examination are given in the CTP Flow Chart.*

Study measurements and assessments scheduled to occur 'before' trial medication administration on Day 1 are to be performed and completed within a 3 h-period prior to the trial oral drug administration.

The acceptable deviation from the scheduled time for vital signs, ECG and laboratory tests will be ± 30 min for the first 4 hours after oral drug administration and ± 45 min thereafter.

Adherence to time windows will be checked via the consistency check listings at the RPM/DBLM.

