7.8.1 Adverse events

AEs will be coded with the most recent version of MedDRA.

The analyses of AEs will be descriptive in nature and will be based on BI standards as presented in the corporate guideline: “Analysis and Presentation of Adverse Event Data from Clinical Trials” [001-MCG-156] ([8](#)).

The standard AE analyses will be based on the number of subjects with AEs (and not on the number of AEs).

For analysis multiple AE occurrence data on the CRF will be collapsed into an AE provided that all of the following applies:

- All AE attributes are identical (LLT, intensity, action taken, therapy required, seriousness, reason for seriousness, relationship, outcome, AE of special interest)
- The occurrences were time-overlapping or time-adjacent (time-adjacency of 2 occurrences is given if the second occurrence started within one hour after end of the first occurrence).

For further details on summarization of AE data, please refer to [001-MCG-156] ([8.4](#)).

Section 5.2.2.1 of the CTP: *The following are considered as AESIs:*

- Hepatic injury

A hepatic injury is defined by the following alterations of hepatic laboratory parameters:

- *an elevation of AST and/or ALT ≥ 3 -fold ULN combined with an elevation of total bilirubin ≥ 2 -fold ULN measured in the same blood sample, and/or*
- *aminotransferase (ALT, and/or AST) elevations ≥ 10 fold ULN*

These lab findings constitute a hepatic injury alert and the patients showing these lab abnormalities need to be followed up according to the 'DILI checklist' provided in the ISF. In case of clinical symptoms of hepatic injury (icterus, unexplained encephalopathy, unexplained coagulopathy, right upper quadrant abdominal pain, etc.) without lab results (ALT, AST, total bilirubin) available, the Investigator should make sure these parameters are analysed, if necessary in an unscheduled blood test. Should the results meet the criteria of hepatic injury alert, the procedures described in the DILI checklist should be followed.

The analysis of adverse events will be based on the concept of treatment emergent adverse events.

Section 5.2.2.2 of the CTP:

The REP refers to the oral drug administration. The REP of the BI 409306 (13-C/15-N) is considered to be negligible. Therefore, all AEs that occur through the treatment phase and throughout the REP will be considered as on treatment (without differentiation of intravenous or oral administration) [...].

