All adverse events occurring before first drug administration will be assigned to 'screening', those between intake of trial medication and end of the 24-hour REP will be assigned to treatment ('on treatment'). AEs occurring after the REP but prior to termination date will be assigned to 'follow-up'.

For more detail see the TSAP ADS plan.

According to ICH E3 (9), AEs classified as 'other significant' need to be reported and will include those non-serious and non-significant adverse events with

- (i) 'action taken = discontinuation' or 'action taken = reduced', or
- (ii) marked haematological and other lab abnormalities or lead to significant concomitant therapy as identified by the Clinical Monitor/Investigator at the Report Planning Meeting.

An overall summary of AEs (including AESIs) will be presented.

The frequency of subjects with AEs will be summarised by treatment (BI tab + iv), primary system organ class (SOC) and preferred term (PT). Separate tables will be provided for subjects with other significant AEs according to ICH E3 (9), for subjects with serious AEs, for subjects with drug-related AEs, for subjects with drug related serious adverse events and for subjects with AESIs.

The SOC and PTs will be sorted by frequency. The MedDRA version number will be displayed as a footnote in the respective output.

In addition, frequencies of subjects with non-serious AEs that had an incidence of > 5% for at least one treatment will be summarised by treatment, primary SOC and PT.

For disclosure of adverse events on EudraCT, additional information not included in a standard AE analysis will be performed. The following three entries will be created:

- Adverse Events per arm for disclosure on EudraCT
- Non-serious Adverse Events for disclosure on EudraCT
- Serious Adverse Events for disclosure on EudraCT

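### Does closing the on-treatment phase at 24 hours hide adverse events found at the end-of-trial examination?

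*SAP*

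**What the plan says.** SAP 6.1 defines three phases for adverse events: screening, on treatment and follow-up. AEs are "counted for treatment if they occur up to the end of the residual effect period (REP) of 24 hours after oral administration". Follow-up is the phase "ranging from end of on treatment phase until 0:00 h on the day after trial termination date". SAP 7.8.1 repeats the rule: "AEs occurring after the REP but prior to termination date will be assigned to" follow-up.

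SAP 6.1 then plans two kinds of display.

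- **Display A** covers CTR Section 15.3 and the registry part of Appendix 16.1.13.1.8. It shows the on-treatment phase only: "Screening and follow-up periods will not be included in this analysis".
- **Display B** covers CTR Section 15.4 and the rest of that appendix. It shows all three phases, and the appendix tables add "a total over all study phases".

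SAP 7.8.1 also plans separate tables for several classes of event, ending with those "for subjects with drug related serious adverse events and for subjects with AESIs". It does not say which phases or which CTR section these tables belong to. Hepatic injury is the only AESI, and it rests on laboratory values: "A hepatic injury is defined by the following alterations of hepatic laboratory parameters".

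**The concern.** The schedule puts two safety assessments at or beyond the 24 h boundary. Under footnote 4 of the protocol Flow Chart, end-of-trial activities follow formal discharge, and protocol 6.2.2 keeps subjects under surveillance for at least 24 h. The only post-dose physical examination (protocol 5.2.5.2) therefore comes at or after the cut-off. The only post-dose safety laboratory (protocol Table 5.2.3: 1) is drawn with the nominal 24:00 sample, so a slightly late draw falls beyond it. Protocol 5.2.2.2 requires clinically relevant changes in either to be recorded as AEs.

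Taken together with Display A, this suggests that abnormalities first detected at the end-of-trial visit would be left out of the main AE tables and the public record. In a trial of at most 12 subjects, even one such event would be visible in the incidence. At stake would be a safety summary that looks cleaner than the data.

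**Working it through.** The plan has no figure of its own to reproduce here beyond the 24 h limit. The check has three parts: the timeline, where a late event is reported, and the weight of one event.

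**1. Timeline**

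Inputs: oral dose at 08:00 on day 1 (Flow Chart, approximate clock time); residual effect period 24 h (SAP 6.1); follow-up to 0:00 on the day after termination (SAP 6.1), with termination on day 2.

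- End of on-treatment phase: 08:00 + 24 h = 08:00 on day 2.
- Length of follow-up: 08:00 on day 2 to 0:00 on day 3 = 16 h.
- Physical examination: after discharge, so at 24:00 post-dose or later.
- Laboratory draw: nominally 24:00, so a finding dated to an on-time draw is still on treatment. The tolerance in SAP 6.7 is ±30 min "for the first 4 hours after oral drug administration and ± 45 min thereafter". If it governs this draw, the permitted range is 24:00 ± 0:45 = 23:15 to 24:45, with 45 of the 90 minutes after the cut-off.

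The last step is doubtful. Protocol 6.1 and SAP 6.7 say separately that the windows for the end-of-trial examination are in the Flow Chart, and its end-of-trial row gives the time as not applicable. The 24:00 time comes only from footnote 4. The 45 minutes are thus a conditional upper limit.

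**2. Where an event with onset after 24:00 is reported**

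| Output | Late event shown? | Source |
|---|---|---|
| CTR 15.3 | No | SAP 6.1, Display A |
| Registry displays | No | SAP 6.1, Display A |
| CTR 15.4 | Yes, under follow-up | SAP 6.1, Display B |
| Appendix 16.1.13.1.8, non-registry part | Yes, under follow-up and in the total | SAP 6.1, Display B |
| Separate listing of SAEs, other significant AEs and AESIs | Yes if it belongs to one of these classes; no phase limit stated | Protocol 7.3.3 |
| End-of-trial laboratory values | Yes: descriptive statistics, shift tables, flagged listings | SAP 7.8.2 |
| Individual listings of all subjects | Yes, Appendix 16.2 | SAP 7 |

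An AESI must also reach the sponsor within 24 hours (protocol 5.2.2.2), whatever phase it is tabulated under.

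The two documents agree. Protocol 5.2.2.2 counts events through the residual effect period as on treatment and later ones as follow-up. Protocol 7.3.3 repeats this and places AEs by recorded onset. SAP 6.1 and 7.8.1 carry it out. Protocol 6.2.2 and 6.2.3 give the short half-life as the reason for holding the end-of-trial examination on day 2, which fits a short residual effect period.

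**3. Weight of one omitted event**

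N is 6 to 12 (protocol 7.6). One subject whose only event of a given kind is dated after 24:00 lowers the incidence in Display A by 1/N:

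- N = 12: 1/12 = 8.3 percentage points.
- N = 6: 1/6 = 16.7 percentage points.

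The documents give no rate for such events. With an assumed per-subject probability p, the chance of at least one affected subject is 1 − (1 − p)^N:

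| Assumed p | N = 6 | N = 12 |
|---|---|---|
| 1% | 5.9% | 11.4% |
| 5% | 26.5% | 46.0% |
| 10% | 46.9% | 71.8% |

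These rates are illustrations only. They show that the answer cannot rest on such events being rare. It rests on part 2: if one occurs, it is reported.

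**The case for a change.** The best case for the concern is that a registry reader sees only Display A. For that reader, a finding dated to the day-2 examination is not shown. No planned display gives all post-dose events without screening, because the appendix total includes screening. There is also an awkward edge in protocol 7.3.3: measurements are assigned by planned time but AEs by recorded onset. Taking 24:00 as planned, a sample drawn at 24:20 could give an on-treatment laboratory value and a follow-up AE. One extra summary would be cheap.

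The description of Display A stands, but little follows from it. Limiting treatment-emergent displays to a prespecified residual effect period is a deliberate choice, and these displays are the ones SAP 6.1 reserves for it. Display B shows follow-up apart from screening, and with at most 12 subjects the individual listings let a reader combine the two post-dose phases. The 24:20 case needs three things: a late draw, a result judged clinically relevant, and an onset entered as the time of the draw. Even then the laboratory value is tabulated and the AE appears in 15.4. An added summary would also bring events from beyond the residual effect period into displays meant to exclude them.

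**Conclusion.** The concern does not hold. The 24 h rule is stated in advance and is consistent between protocol and SAP. Followed as written, it removes no event from the clinical trial report. Safety is descriptive only (protocol 5.2.1), so no test or decision depends on which table carries a late event, and the primary pharmacokinetic analysis is untouched.

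The remainder is a preference about layout. An event with onset dated after 24:00, within a follow-up phase of about 16 h, appears in 15.4 and the appendix but not in 15.3 or the registry displays. Each subject with no other event of that kind counts for 8.3 to 16.7 percentage points there. The number of such subjects cannot be derived and may be zero.

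Even that remainder rests on assumptions the documents do not settle:

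- Onset is entered as the time of detection or draw. Protocol 5.2.2.2 asks for the time of onset but does not say how to set it for examination or laboratory findings. A symptom reported at the visit that began within 24 h stays on treatment.
- The separate ADS plan, to which the SAP refers for detail, keeps the 24 h boundary.
- For AESIs, the table in SAP 7.8.1 follows the on-treatment rule, which is not stated.

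Whether 24 h suits the drug pharmacologically was not tested, because the protocol and SAP text reviewed here gives no half-life value.

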6.2 IMPORTANT PROTOCOL VIOLATION

Data discrepancies and deviations from the CTP will be identified for all randomised subjects. Listings of protocol deviations and of unresolved discrepancies will be provided to be discussed at the combined report planning and database lock meeting (RPM/DBLM), e.g. deviations in drug administration, in blood sampling etc. At this meeting, it will be decided whether the discrepant data can be used as they are or whether the data have to be corrected in the clinical database.

Each protocol deviation must be assessed to determine whether it is an important protocol violation. A protocol violation (PV) is important if it affects the rights or safety of the study subjects or if it can potentially influence the primary outcome measure(s) for the respective subjects in a way that is neither negligible nor in accordance with the study objectives. This last category of important PV forms the basis for the decision of whether a subject does or does not belong to an analysis set. PVs that do not influence the subject's rights and safety or the evaluability of the subjects for the main study objectives are called non-important PVs. These are only considered when checking the trial quality in general.

If any important PVs are identified, they are to be summarised into categories and will be captured in the RPM/DBLM minutes via an accompanying Excel spreadsheet [001-MCS-50-

413_RD-02] (2). The following table contains the categories which are considered to be important protocol violations in this trial. If the data show other important PVs, this table will be supplemented accordingly by the time of the RPM/DBLM.

Table 6.2: 1 Important protocol violations

Category /Code	Description
A	Entrance criteria not met
	A1 Inclusion criteria violated
	A2 Exclusion criteria violated
B	Informed consent
	B1 Informed consent not available
	B2 Informed consent too late
C	Trial medication and randomisation
	C1 Incorrect trial medication taken
	C2 Non-compliance
D	Concomitant medication
	D1 Concomitant medication with the potential to affect the assessment of the trial medication
E	Missing data
	E1 Certain violations of procedures used to measure primary data
F	Incorrect timing¹
	F1 Certain violations of time schedule used to measure primary data
G	Other trial specific important violations
	G1 PVs affecting safety and rights

¹ Time deviations will only be flagged as important PV, when leading to exclusion of the entire subject from an analysis set
Source: 'Protocol Violation Handling Definitions' [001-MCS-50-413_RD-01] (3)

6.3 PATIENT SETS ANALYSED

- Treated set (TS):

This subject set includes all subjects who were documented to have received at least one dose of study drug.

This is the full analysis set population in the sense of ICH-E9 ([1](#)).

It is used for safety analyses.

Section 7.3.1 of the CTP: *Plasma concentration data and parameters of a subject will be included in the statistical pharmacokinetic (PK) analysis if they are not flagged for exclusion due to a protocol violation relevant to the evaluation of PK (to be decided no later than in the Report Planning Meeting) or due to PK non-evaluability (as revealed during data analysis, based on the criteria specified below). Exclusion of a subject's data will be documented in the CTR.*

Relevant protocol violations may be:

- *Incorrect trial medication taken, i.e. the subject received at least one dose of trial medication the subject was not assigned to*
- *Incorrect dose of trial medication taken*
- *Use of restricted medications.*

Plasma concentrations and/or parameters of a subject will be considered as non-evaluable, if for example:

- *the subject experiences emesis that occurred at or before 2 times median t_{max} of the respective treatment (Median t_{max} is to be determined excluding the subjects experiencing emesis),*
- *a pre-dose concentration is >5% C_{max} value of that subject*
- *missing samples/concentration data at important phases of PK disposition curve*
- **PK parameter analysis set (PKS):**
This subject set includes all subjects from the TS who provide at least one primary PK parameter that was not excluded according to the description above. Thus, a subject will be included in the PKS, even if he/she contributes only one PK parameter value for one formulation to the statistical assessment.

The descriptive analysis of PK concentrations will be based on the analysis data set (ADS) ADPC as described at the beginning of [Section 7](#).

Table 6.3: 1 Subject sets analysed

Class of endpoint	Analysis set	
	TS	PKS
Analyses of PK endpoints		X
Safety endpoints	X	
Demographic/baseline endpoints	X	
Important protocol violations	X	
Disposition	X	

6.5 POOLING OF CENTRES

This section is not applicable, because the study was performed in only one centre.

6.6 HANDLING OF MISSING DATA AND OUTLIERS

Data of screened subjects who were withdrawn from the trial prior to first administration of any study drug will not be reported in the CTR.

Handling of missing data and outliers will be performed as described in the CTP, Section 7.4.

The only exception where imputation might be necessary for safety evaluation are AE dates. Missing or incomplete AE dates are imputed according to BI standards (see 001-MCG-156_RD-01 ([4](#))).

Missing data and outliers of PK data are handled according to BI standards (see 001-MCS-36-472_RD-01 ([5](#))).

6.7 BASELINE, TIME WINDOWS AND CALCULATED VISITS

For vital signs and laboratory parameters the baseline is defined as the last measurement prior to first study drug administration.

Section 6.1 of the CTP: *Exact times of measurements outside the permitted time windows will be documented. The acceptable time windows for screening and end-of-trial examination are given in the CTP Flow Chart.*

Study measurements and assessments scheduled to occur 'before' trial medication administration on Day 1 are to be performed and completed within a 3 h-period prior to the trial oral drug administration.

The acceptable deviation from the scheduled time for vital signs, ECG and laboratory tests will be ± 30 min for the first 4 hours after oral drug administration and ± 45 min thereafter.

Adherence to time windows will be checked via the consistency check listings at the RPM/DBLM.

